4 PATIENT SELECTION

The criteria for inclusion and exclusion are defined below:

4.1 Inclusion Criteria

- 1) Male and female subjects at least 12 years of age
- 2) Presence of clinical signs and/or symptoms consistent with an acute illness compatible with influenza infection (each of the following is required):
 - a) oral temperature of $\geq 99.4^{\circ}\text{F}$ or $\geq 37.4^{\circ}\text{C}$ (obtained in office or self-measured within 12 hours prior to screening – if self-measured, subject must also have taken an antipyretic within 4 hours prior to screening), AND
 - b) at least one of the following respiratory symptoms (cough, sore throat, nasal obstruction), AND
 - c) at least one of the following constitutional symptoms (fatigue, headache, myalgia, feverishness).
- 3) Confirmation of influenza A or B infection in the local community by one of the following means: (a) the institution's local laboratory, (b) the local public health system, (c) the national public health system, or (d) a laboratory of a recognized national or multinational influenza surveillance scheme

- 4) Onset of illness no more than 40 hours before enrollment in the trial
Note: Time of onset of illness is defined as the earlier of:
 - a) the time when the temperature was first measured as elevated, OR
 - b) the time when the subject experienced the presence of at least one respiratory symptom AND the presence of at least one constitutional symptom.
- 5) Willing and able to provide written informed consent (including assent by legal guardian if under 18 years of age) and comply with the requirements of the protocol, including completion of the patient diary

4.2 Exclusion Criteria

- 1) Severity of illness requiring or anticipated to require in-hospital care
- 2) Moderate or severe asthma (Global Initiative for Asthma (GINA) 2017 classification)
- 3) Cystic fibrosis
- 4) Stage II, III or IV chronic obstructive pulmonary disease (COPD) (Global Initiative for Chronic Obstructive Pulmonary Disease (GOLD) 2017 classification)
- 5) NYHA Class III or IV congestive heart failure (at least marked limitation of physical activity in which minimal ordinary activity results in fatigue, palpitation, dyspnea, or angina pain)
- 6) Cardiac arrhythmia
- 7) Immunologic disorders or receiving immunosuppressive therapy (e.g., for organ or bone marrow transplants, immunomodulatory therapies for certain autoimmune diseases)
- 8) Untreated HIV infection or treated HIV infection with a CD4 count below 350 cells/mm³ in the last 6 months
- 9) Persons with sickle cell anemia or other hemoglobinopathies
- 10) Poorly controlled insulin-dependent diabetes mellitus (HbA1C >8.0%)
- 11) Residents of any age of nursing homes or other long-term care institutions
- 12) Concurrent infection at the screening examination that requires systemic antimicrobial therapy
- 13) Females of childbearing potential who are either pregnant, breast-feeding or are sexually active without the use of birth control. Female subjects of child-bearing potential that are sexually active must have a negative baseline pregnancy test and must agree to continue an acceptable method of birth control for the duration of the study and for 1 month post-treatment. A double barrier method, oral birth control pills administered for at least 2 monthly cycles prior to study drug administration, an IUD, or medroxyprogesterone acetate administered intramuscularly for a minimum of one month prior to study drug administration are acceptable methods of birth control for inclusion into the study. Female subjects are considered of childbearing potential unless they are postmenopausal (absence of menstrual bleeding for 1 year - or 6 months if laboratory confirmation of hormonal status), or have had a hysterectomy, bilateral tubular ligation or bilateral oophorectomy.

- 14) Receipt of any dose of NTZ, oseltamivir, zanamivir, peramivir, laninamivir, baloxavir, amantadine or rimantadine within 3 days prior to screening
- 15) Prior treatment with any investigational drug therapy within 30 days prior to screening
- 16) Subjects with active respiratory allergies or subjects expected to require anti-allergy medications during the study period for respiratory allergies
- 17) Known sensitivity to NTZ or any of the excipients comprising the NTZ tablets
- 18) Subjects unable to take oral medications
- 19) Presence of any pre-existing illness or condition that, in the opinion of the Investigator, would place the subject at an unreasonably increased risk through participation in this study
- 20) Subjects who, in the judgment of the Investigator, will be unlikely to comply with the requirements of this protocol

5 STUDY PROCEDURES

5.1 Screening Evaluation (day 1)

Before screening, subjects and their parents/guardian(s) will be informed of the nature of study, and written consent must be obtained prior to participation. After giving informed consent, the subject will be assigned a subject number, and the following procedures will be carried out:

- 1) Complete medical history;
- 2) Full physical examination including body weight and vital signs (blood pressure, pulse, respiratory rate and oral temperature using standard electronic oral thermometer provided by Sponsor);
- 3) Collection of demographic information and smoking history;
- 4) Urine pregnancy test for all females of childbearing potential;
- 5) Recording of symptoms and time of onset; and
- 6) Evaluation according to eligibility (inclusion and exclusion) criteria.

While not required by this study protocol, local influenza diagnostic testing may have been conducted prior to the screening visit in accordance with local standards of care. Results of any such local influenza diagnostic tests will not impact subject selection. Subjects will be selected solely on the basis of the eligibility criteria set forth in the protocol irrespective of the result of any local influenza diagnostic test that may have been performed.

5.2 Baseline (day 1, same day as screening evaluation)

At baseline, the following procedures will be carried out:

- 1) Collection of two nasopharyngeal swabs (one from each nostril) using nylon flocked dry swabs (Copan Diagnostics) for RT-PCR and culture;

- 2) Collection of blood sample for anti-influenza antibodies;
- 3) Collection of blood sample for laboratory safety tests including hemoglobin, hematocrit, complete blood count (total and differential), platelet count, random blood sugar, total cholesterol, HDL, LDL, triglycerides, albumin, AST, ALT, GGT, alkaline phosphatase, bilirubin (total/direct), BUN, creatinine, sodium, potassium, chloride;
- 4) Collection of a urine sample for routine urinalysis (glucose, protein and blood);
- 5) Review and recording of any concomitant medications;
- 6) Provision of an electronic diary to subject via his/her own smartphone or a provisioned device, and subject completion of baseline electronic diary under supervision and instruction of study site personnel;
- 7) Randomization and dispensing of study medication (medication assigned in sequential order);
- 8) Administration of the first dose of study medication with food (< 1 hour after food intake) under observation of Investigator or a member of Investigator's staff, and entry in diary; and
- 9) Instruct subject regarding:
 - a. *Administration of study medication.* Subjects will be instructed to take the study medication (two tablets) twice daily with food (< 1 hour after food intake). The patient should take his/her second dose as close as possible to 12 hours after the first dose. Then he/she will take the study medication every 12 hours for the remaining 4 days.
 - b. *Concomitant medications.* Subjects will be instructed that they may take acetaminophen for fever if their oral temperature is $\geq 100.4^{\circ}\text{F}$ (38°C). No other symptom relief medication should be used.
 - c. *Completion of patient diary.* Subjects will be instructed on completion of the electronic diary.
 - d. *Use of birth control.* Female subjects of childbearing potential, if sexually active, will be instructed to continue an acceptable method of birth control for the duration of the study and for 1 month post-treatment. Acceptable methods of birth control include a double barrier method, oral birth control pills, an IUD, or medroxyprogesterone acetate administered intramuscularly.
 - e. *Follow-up visits:* Patients will be instructed to return to the clinic for follow-up on day 7 and day 22.
 - f. *Seeking emergency care or contacting the study physician or nurse:* Subjects must be informed to seek emergency medical care or contact the study physician or nurse if they develop any of the following symptoms listed below during the full 22 day study and follow-up period.

CALL 911 (United States) OR LOCAL EMERGENCY SERVICES (outside of United States) OR HOSPITAL OR CONTACT STUDY PHYSICIAN, IF:

- Trouble breathing including shortness of breath.
- Severe headache, stiff neck, confusion or excessive somnolence.

CALL STUDY NURSE OR PHYSICIAN, IF:

- Extremely high fever $>104^{\circ}\text{F}$ (40°C).

- Fever ($\geq 100.4^{\circ}\text{F}$ or $\geq 38^{\circ}\text{C}$) lasts for longer than 3 days.
- Increased difficulty breathing.
- Wheezing develops.
- New pain develops or pain localizes to one area, such as an ear, the throat, the chest, or the sinuses.
- Symptoms become more severe or frequent.
- Fever ($\geq 100.4^{\circ}\text{F}$ or $\geq 38^{\circ}\text{C}$) returns after being absent for 24 hours.
- Symptoms recur or any difficulty breathing following 5-10 days resolution of influenza.
- An allergic-like reaction occurs or is suspected
- Abnormal behavior

10) Review and record adverse events.

5.3 Day 2 – Day 22

A study physician, nurse or other site personnel will review each subject's electronic diary entries daily to ensure compliance with collection of diary data. If a subject has not completed his/her diary or if errors are suspected, the study personnel will contact the subject to implement appropriate corrective actions.

5.4 Day 2-5 Telephone Monitoring

A study physician, nurse or other site personnel will make daily telephone calls to subjects on each of days 2, 3, 4 and 5 of dosing to review compliance with study medication, review symptoms, screen for influenza-related complications including sinusitis, otitis, bronchitis, pneumonia, central nervous system disease and worsening of pre-existing health conditions, and review adverse events. Subjects will be referred for immediate care as needed based on the screening. All information gained from telephone monitoring will be included in the case report forms for each subject. [Note: In lieu of a telephone call, this information may be obtained during the day 2 and 3 home or office visits (see below).]

5.5 Day 2 and 3 Evaluations

A study physician, nurse or other study personnel will visit each subject at home (or at the clinic or another location as agreed with the subject) on each of days 2 and 3 to (i) collect two nasopharyngeal swabs for detecting (RT-PCR) and quantifying (TCID_{50}) influenza virus, and (ii) review symptoms and screen for influenza-related complications including sinusitis, otitis, bronchitis, pneumonia, central nervous system disease and worsening of pre-existing health conditions as well as adverse events. Subjects will be referred for immediate care as needed based on the screening. All information gained from these visits will be included in the case report forms for each subject. In addition, a blood sample for pharmacokinetics will be collected on day 3. The day 2 and day 3 visits will occur at approximately the same time of day that the patient took his/her first dose of study medication (approximately 24 and 48 hours after the first dose). On day 3, the blood sample for pharmacokinetics will be collected before the first dose of that day.

Study sites or subjects may opt out of these day 2 and day 3 visits due to site staffing, patient availability or other practical considerations or preferences; nevertheless at least 75% of subjects enrolled in the trial are expected to complete the day 2 and day 3 visits and related procedures (for viral kinetics and pharmacokinetics).

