the same time of day that the subject took his/her first dose of study medication (roughly 24 and 48 hours post-first dose). On day 3, the blood sample for pharmacokinetics will be collected before the dose. The nasopharyngeal swabs will be used to evaluate quantitative changes in viral shedding. The blood samples will be used to evaluate relationships between pharmacokinetics and virologic or clinical response. Study sites or subjects may opt out of the day 2 and day 3 visits due to site staffing, patient availability or other practical considerations or preferences; nevertheless, at least 75% of subjects enrolled in the trial are expected to complete the day 2 and day 3 visits and related procedures (for viral kinetics and pharmacokinetics).

A study physician, nurse or other site personnel will make daily telephone calls to subjects for the first five days of dosing to review symptoms and screen for influenza-related complications including sinusitis, otitis, bronchitis, pneumonia and central nervous system disease. Subjects will be referred for immediate care as needed based on the screening. [Note: In lieu of a telephone call, this information may be obtained during the day 2 or 3 office or home visits (see the preceding paragraph).] The study sites and subjects will be blinded from virology laboratory data until after study day 22 or, if earlier, until the subject is discontinued from the study. During the study period, each subject will be presumed to have influenza infection, and any worsening of symptoms or complications will be presumed to be influenza-related.

Subjects will return to the clinic on days 7 and 22 for post-treatment follow-up, including two nasopharyngeal swabs, drug accountability, reporting of adverse events and complications of influenza. Blood and urine samples for laboratory safety tests will be collected at day 7, and a blood sample for anti-influenza antibodies will be collected on day 22. A nurse or other study personnel will review the electronic patient diary entries daily (synchronized to a web-based data system) to ensure contemporaneous and complete recording of diary data. Subjects will maintain the electronic patient diaries until study day 22. Any visits that do not occur on the prescribed date, or within 1 day of that date in the case of the day 7 visit or within 3 days after that date in the case of the day 22 visit, will be recorded as protocol deviations.

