8.4.3 Population Pharmacokinetics Analysis

On day 3, the plasma samples will be collected before the morning dose (at the trough). This data will allow for analysis of relationships between trough plasma concentrations and clinical and virologic response.

Day 3 trough plasma concentrations of tizoxanide and tizoxanide glucuronide will be summarized descriptively for each of the treatment groups. Exploratory analyses will be conducted to evaluate relationships between plasma concentrations and age, race, gender, body weight, body mass index, concomitant medications, changes in viral titer over time, time from first dose to Symptom Response and adverse events.

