7.2 Study Design

The study will be a multicenter, randomized, double-blind trial to evaluate the efficacy of NTZ compared to placebo in treating uncomplicated influenza. Subjects will be selected according to the inclusion and exclusion criteria listed in the protocol. The study is designed to enroll at least 600 subjects (up to 700 maximum) with laboratory-confirmed influenza. Total enrollment required to achieve this number is expected to be approximately 800 to 1200 subjects. Prior to screening for inclusion in the study, informed consent will be obtained.

Immediately after completion of informed consent, screening, and enrollment in the study, two baseline nasopharyngeal swabs will be collected for viral culture and RT-PCR. A blood sample will be collected for laboratory safety tests and anti-influenza antibodies, and a urine sample will be collected for laboratory safety tests. Subjects will receive instruction on completing their electronic diaries, recording concomitant medications and attending follow-up visits.

Then subjects will be randomized 1:1 to one of the following groups:

- Group 1 (NTZ): Two NTZ 300 mg tablets b.i.d. for 5 days
- Group 2 (Placebo): Two placebo tablets b.i.d. for 5 days

The medication will be taken in the morning and evening with food. The first dose will be taken with food in the physician's office under the observation of the Principal Investigator or a member of the Investigator's staff. The second dose will be taken by the patient as close as possible to 12 hours after the first dose.

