10.6.2 Population Pharmacokinetics Analysis

Variables Used for the Analysis

The analysis will require the following variables:

Variable	Source	Format/Notes
Day 3 tizoxanide (T) and tizoxanide glucuronide (TG) values	Laboratory data	
Demographic data	CRF	
Concomitant medications use	CRF	
Adverse events	CRF	

Analysis

Plasma concentrations of T and TG will be summarized descriptively for both treatment groups. Exploratory analyses will be conducted to evaluate relationships between plasma concentrations and age, race, gender, body weight, body mass index, concomitant medications (yes/no), changes in viral titer over time, Time to Symptom Response, and adverse events (yes/no). For continuous factors, the relationship with plasma concentrations will be assessed by Spearman’s correlation analysis and Pearson’s correlation analysis. For categorical factors, plasma concentrations will be compared among groups using the Kruskal-Wallis test.

Analysis Population(s):	Confirmed Influenza, NTZ-treated only
Derived Variables:	
 • Concomitant medications use: if any concomitant medication is used, then “yes”, otherwise “no” • Adverse events: if any adverse event is reported, then “yes”, otherwise “no” • Changes in viral titer over time: see section 10.5.5 • Time to Symptom Response: see section 10.2

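### For an afternoon first dose, the Day 3 pharmacokinetic timing statements cannot all be met, and the SAP plans no time-since-last-dose variable to show which samples are troughs

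*Protocol*

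**What the plan says.** The first dose is taken in the office on the day of screening (Protocol 3 and 5.2). No passage restricts it to the morning.

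- **Visit time.** Of the Day 2 and Day 3 visits, Protocol 5.5 says that each "will occur at approximately the same time of day that the patient took his/her first dose of study medication". It gives the interval as "approximately 24 and 48 hours after the first dose".
- **Sample time.** Protocol 3 puts the Day 3 sample before the dose, without saying which dose. Protocol 5.5 is more specific: "On day 3, the blood sample for pharmacokinetics will be collected before the first dose of that day". Protocol 8.4.3 reads "On day 3, the plasma samples will be collected before the morning dose (at the trough").
- **Dose times.** Protocol 5.2 puts the second dose about 12 hours after the first and continues: "Then he/she will take the study medication every 12 hours for the remaining 4 days". SAP 7.2 says: "The medication will be taken in the morning and evening with food".
- **Use.** Protocol 8.4.3 relates trough concentrations to clinical and virologic response. In SAP 10.6.2, "Exploratory analyses will be conducted to evaluate relationships between plasma concentrations and age, race, gender, body weight, body mass index", as well as viral titer change, Time to Symptom Response and adverse events.
- **Recording.** The electronic diary captures medication intake when it happens (Protocol 5.10). The variables in SAP 10.6.2 include neither collection time nor time since last dose. The concentration listing in SAP Table 6 (display 16.2.8.4) gives visit, date and the two concentrations.

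**The concern.** A concentration can be read as a trough only if the time since the previous dose is known and close to the dosing interval. Here the visit is tied to the clock time of enrollment, while the sample is tied to the day's first or morning dose. For a subject enrolled in the afternoon these anchors separate, and a site must decide for itself which statement to follow. Different sites may decide differently.

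Day 3 is the only concentration sample in the schedule, and at least 75% of subjects are expected to complete the visit. Relating pharmacokinetics to clinical or virologic response is among the stated study objectives. If values taken at different times after dosing are pooled as troughs, the summary level may shift in either direction. The concentration-response and covariate relations would then carry variation that comes from enrollment hour rather than from exposure.

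**Working it through.** **1. The plan's own timing under 12-hourly dosing.** Doses fall at 0, 12, 24, 36 and 48 hours, and so on. Since 48 = 4 × 12, the visit coincides with a scheduled dose. A sample taken just before that dose is 48 − 36 = 12 hours after the previous one, whatever the clock time of the first dose.

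**2. Do the other statements hold at that moment?**
- First dose at 10:00: doses at 10:00 and 22:00. The 48-hour sample precedes the first dose of the day, which is also the morning dose. All statements agree.
- First dose at 14:00: doses at 02:00 and 14:00. The 48-hour sample at 14:00 is a 12-hour trough. It precedes the second dose of that calendar day and no morning dose, and the schedule is not morning and evening. The statements cannot all be met.

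**3. What if dosing moves to morning and evening?** Assume 08:00 and 20:00. These times are not in the documents. Let the first dose, and so the visit, be at hour h. Time since last dose is h − 8 if the Day 3 morning dose has been taken, or h + 24 − 20 = h + 4 if it is held until the visit.

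| First dose | 12-hourly | Morning dose taken | Morning dose held |
|---|---|---|---|
| 10:00 | 12 h | 2 h | 14 h |
| 12:00 | 12 h | 4 h | 16 h |
| 14:00 | 12 h | 6 h | 18 h |
| 16:00 | 12 h | 8 h | 20 h |

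**4. What that could mean for the values.** Inputs are the healthy-volunteer means in Protocol 1.2.2.
- Peak against Day 3 trough, tizoxanide: 5.23/2.36 = 2.2 (Day 1 Cmax) and 8.16/2.36 = 3.5 (Day 7 Cmax).
- The same for the glucuronide: 4.88/4.38 = 1.1 and 8.96/4.38 = 2.0.
- Six extra hours at the Day 7 terminal rate, tizoxanide: exp(0.331 × 6) = 7.3-fold lower, leaving about 0.14 of the trough.
- The same for the glucuronide: exp(0.201 × 6) = 3.3-fold lower, leaving about 0.30.

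The peak ratios are upper limits on this basis. Mean Cmax averages each subject's own peak, and tizoxanide tmax ranges from 3 to 8 hours on Day 7, so the mean at a fixed 6 hours would be lower. Dividing by the Day 7 end-of-interval mean instead gives 8.16/1.72 = 4.7, but the trial samples on Day 3. The Day 7 rate is used because the protocol reports steady state by Day 2. The decline past 12 hours is an extrapolation, since sampling in that study stopped at 12 hours.

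**The case against.** The strongest reply is that the protocol's operative dosing rule is every 12 hours. Under that rule step 1 gives a true trough for every subject, and Protocol 3 asks only for a pre-dose sample. This stands. A reader might infer that a 48-hour sample can never be a trough unless the first dose was in the morning, or that the data will contain near-peak values. The documents support neither. A near-peak sample needs two departures: the subject leaves 12-hourly dosing, and the site draws after a dose despite three pre-dose statements. The held-dose case respects the pre-dose wording but breaks the 12-hour interval, and no passage instructs it.

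Leaving strict 12-hourly dosing is nevertheless foreseeable. A 14:00 start implies a 02:00 dose soon after food, the bottle label says only twice daily with food, and the SAP itself describes morning and evening dosing. The SAP does not instruct subjects, however, and visits may take place at home at an approximate time, which gives sites some room.

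A second reply is that listing columns are not the database. Layouts are approved separately (SAP 8.2), information from the visit goes into the case report form (Protocol 5.5), and dose times are in the diary. This also stands. It cannot be said that trough and non-trough samples are indistinguishable in the source data, only that the planned analysis and listing do not separate them. SAP 10.6.2 also speaks of plasma concentrations; the trough label comes from Protocol 8.4.3.

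Finally, a numerical bias in the mean trough or in the correlations could be calculated only by supposing a share of mistimed samples. The documents give no clinic hours or other basis for that share, so no such figure is offered.

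**Conclusion.** The inconsistency is real but conditional. For afternoon first doses, the visit time, the two specific sampling statements, 12-hourly dosing and the SAP's morning and evening dosing cannot all be satisfied. Strict 12-hourly dosing still yields a 12-hour trough. If dosing shifts, or a dose is held for the visit, some values treated as troughs may be well short of or well beyond 12 hours. For tizoxanide the illustrative range runs from at most about 2.2 to 3.5 times the Day 3 trough down to about one seventh of it; the glucuronide moves less. This rests on assumed 08:00 and 20:00 dosing, healthy-volunteer means and log-linear decline past 12 hours. The number of subjects affected is unknown and may be small.

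The planned outputs would not reveal the problem. Its reach is limited to the exploratory pharmacokinetic analyses: the primary and secondary efficacy analyses, the testing hierarchy and the sample size are unaffected. It is worth correcting because the correction is cheap and serves a stated objective.

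**What to change.** - Reconcile the dosing-time and sampling-time statements in Protocol 3, 5.2, 5.5 and 8.4.3 and SAP 7.2, including what applies when the first dose is in the afternoon. Which rule should govern is for the sponsor to decide; this review takes no position.
- Confirm that the collection time of the Day 3 sample is recorded.
- In SAP 10.6.2, derive time since last dose as collection time minus the last diary dose time.
- Limit analyses described as trough to a window fixed before unblinding (10 to 14 hours after the last dose would be one example of an analysis window). Analyse all samples with time since last dose as a covariate.
- Add collection time and last-dose time to listing 16.2.8.4.

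The cost is a protocol clarification, a few lines of SAP text and, if collection time is not already captured, one field on the Day 3 form. The downside is fewer samples in the trough-only analysis.
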